3.8.3. Management strategy

Management strategies will include active monitoring and intervention (surgery, stereotactic radiosurgery (SRS), fractionated radiotherapy (fRT) or discharge from outpatient clinic care) (Figure 3). **Active monitoring** is defined as regular surveillance imaging and outpatient clinical observation. Recorded factors will include:

- Number of scans, and interval between them (months)
- For each scan: peritumoural signal intensity, venous sinus involvement and meningioma volume
- Each scan will be examined alongside its corresponding outpatient clinic appointment for any evidence of meningioma-related symptoms (motor/sensory/language/cognitive/seizure/headache/other)
- The outcome of each clinical encounter (i.e. outpatient appointment) will be recorded (resume follow-up/surgery/SRS/fRT/hospital discharge)

Intervention details; if performed, will also be recorded. These will include indication for intervention (clinical-radiological/clinical/radiological/patient preference) and time to intervention. For patients treated with clinical-radiological or clinical progression, status of meningioma-related neurological morbidity will be noted.

For surgery, the following will additionally be recorded:

- Simpson grade (as recorded by the surgeon in the operative notes) (21)
- WHO grade (classified according to the WHO system in use at the time of surgery and updated according to the WHO 2016 classification dependent on pathologists' availability (22)) and presence of any reported brain invasion (yes / no / not reported)
- Postoperative medical and surgical complications recorded at 30 days (Landriel-Ibañez Classification (Table 3) (23))
- Follow-up duration (months)
- WHO performance status pre- and postoperatively and at the last follow-up appointment.
- Recurrence on contrast-enhanced MRI during that time (yes/no) and if recurred then the time to recurrence

For SRS and fRT:

- Fractionated dose (fRT), number of fractions (fRT) and total dose (fRT /SRS)
- Early and late (≥ 3 months) toxicity (assessed by CTCAE v5.0, https://ctep.cancer.gov/protocoldevelopment/electronic_applications/ctc.htm)
- Duration of follow-up post-radiation (months)
- WHO performance status pre- and post-radiation and at the last follow-up appointment
- Progression/regrowth on contrast-enhanced MRI during that time (yes/no) and if progressed/regrew then the time to progression/regrowth

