Pharmacological intervention	Checkbox	Prompt entry if previous option (Postoperative surgical complications) has been ticked
Surgical intervention	Dropdown list/checkbox 
 • No • Without GA • Under GA 	Prompt entry if previous option (Postoperative surgical complications) has been ticked
ICU admission	Checkbox	Prompt entry if previous option (Postoperative surgical complications) has been ticked
Organ failure	Dropdown list/checkbox 
 • None • Single-organ • Multi-organ 	Prompt entry if previous option (Postoperative surgical complications) has been ticked. Allow one option only
Persisted with no improvement beyond 30 days?	Checkbox	Prompt entry if previous option (Postoperative surgical complications) has been ticked

Postoperative medical complications	checkbox	Required
Complication	Dropdown list/check box 
 • Myocardial infarction • Arrhythmia • Pneumonia • Pulmonary embolism • Deep venous thrombosis • Urinary tract infection • Acute kidney injury • Other 	Prompt entry if previous option (Postoperative medical complications) has been ticked Allow more than one option
Pharmacological intervention	Checkbox	Prompt entry if previous option (Postoperative medical complications) has been ticked
Surgical intervention	Dropdown list/checkbox 
 • No • Without GA • Under GA 	Prompt entry if previous option (Postoperative medical complications) has been ticked
ICU admission	Checkbox	Prompt entry if previous option (Postoperative medical complications) has been ticked
Organ failure	Dropdown list/checkbox 
 • None • Single-organ • Multi-organ 	Prompt entry if previous option (Postoperative medical complications) has been ticked. Allow one option only
Persisted with no improvement beyond 30 days?	Checkbox	Prompt entry if previous option (Postoperative medical complications) has been ticked
Postoperative WHO PS	Dropdown list/checkbox 
 • 0 • 1 • 2 • 3 • 4 • 5 (dead) 	Required. Allow one option only
Recurrence	Checkbox	Prompt entry if previous option (Postoperative WHO PS) is not 5
Scan date (at recurrence or last follow-up date if no recurrence)	DD/MM/YYYY	Prompt entry if previous option (Postoperative WHO PS) is not 5

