WHO PS at time of recurrence/last follow-up	Dropdown list/checkbox 
 • 0 	Prompt entry if previous option (Postoperative WHO PS) is not 5

	
 • 1 • 2 • 3 • 4 	
SRS (SECTION/PAGE 7)		
Pre-radiation WHO PS	Dropdown list/check box 
 • 0 • 1 • 2 • 3 • 4 	Required entry. Allow one option only
Pre-radiation comorbidity	Check box 
 • Hypertension - systolic > 140 or diastolic > 90 and patients on medical treatment • Previous myocardial infarction • Congestive heart failure • Peripheral vascular disease • Previous stroke/TIA - If hemiplegia present, do not check • Hemi/paraplegia • Diabetes which requires medical treatment • Diabetes with end-organ damage - if so, do not check diabetes that requires treatment • COPD/Asthma • Renal disease • Mild liver disease - Hep B/C or cirrhosis without portal hypertension 	Required entry. Allow multiple options. Note to data collector: Age and comorbidities will be used to calculate the age adjusted Charlson comorbidity index. Each of these is defined in the guide provided

	
 • Moderate to severe liver disease - cirrhosis with portal hypertension, jaundice, ascites • Peptic ulcer disease • Cancer - excluding basal cell carcinoma • Metastatic cancer - if so, do not check cancer • Rheumatic or connective tissue disease • HIV/AIDS • Skin ulcers/cellulitis • Depression • Dementia • On Warfarin 	
Dose	Free field	Required entry
Early CTCAE toxicity (≤3 months)	Checkbox	Required entry
Toxicity	Free field	
Prompt entry if previous option (Early CTCAE toxicity (≤3 months)) is ticked
 
Note to data collector: https://ctep.cancer.gov/protocoldevelopment/electronic_applications/ctc.htm Use the following format: System class organ (SOC)-CTCAE term-grade e.g. nervous system disorders-headache-1. Select the complication with the highest toxicity grade

Late CTCAE toxicity	Checkbox	Required entry
Toxicity	Free field	
Prompt entry if previous option (Late CTCAE toxicity) is ticked
 
Note to data collector: https://ctep.cancer.gov/protocoldevelopment/electronic_applications/ctc.htm Use the following format: System class organ (SOC)-CTCAE term-grade e.g. nervous system disorders-headache-1. Select the complication with the highest toxicity grade

Meningioma progression/regrowth	Checkbox	Required

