Scan date (at progression or last follow-up date if no progression)	DD/MM/YYYY	Required
WHO PS at time of progression/last follow-up	Dropdown list/checkbox 
 • 0 • 1 	Required. Allow one option only

	
 • 2 • 3 • 4 • 5 (dead) 	
fRT (SECTION/PAGE 8)		
Pre-radiation WHO PS	Dropdown list/check box 
 • 0 • 1 • 2 • 3 • 4 	Required entry
Pre-radiation comorbidity	Check box 
 • Myocardial infarction • Congestive heart failure • Peripheral vascular disease • Hemiplegia • Cerebrovascular disease • Pulmonary disease • Diabetes • Renal disease • Liver disease • Peptic ulcer disease • Cancer • Dementia • Connective tissue disease • AIDS • Hypertension • Skin ulcers/cellulitis • Depression • On Warfarin 	Required entry. Allow multiple options. Note to data collector: Age and comorbidities will be used to calculate the age adjusted Charlson comorbidity index. Each of these is defined in the guide provided
Number of fractions	Free field	Required entry
Fractionated dose	Free field	Required entry
Total dose	Free field	Required entry
Early CTCAE toxicity (≤3 months)	Checkbox	Required entry
Toxicity	Free field	Prompt entry if previous option (Early CTCAE toxicity (≤3 months)) is ticked

		Note to data collector: https://ctep.cancer.gov/protocoldevelopment/electronic_applications/ctc.htm Use the following format: System class organ (SOC)-CTCAE term-grade e.g. nervous system disorders-headache-1. Select the complication with the highest toxicity grade
Late CTCAE toxicity	Checkbox	Required entry
Toxicity	Free field	Prompt entry if previous option (Late CTCAE toxicity) is ticked Note to data collector: https://ctep.cancer.gov/protocoldevelopment/electronic_applications/ctc.htm Use the following format: System class organ (SOC)-CTCAE term-grade e.g. nervous system disorders-headache-1. Select the complication with the highest toxicity grade
Meningioma progression/regrowth	Checkbox	Required
Scan date (at progression or last follow-up date if no progression)	DD/MM/YYYY	Required
WHO PS at time of progression/last follow-up	Dropdown list/checkbox 
 • 0 • 1 • 2 • 3 • 4 • 5 (dead) 	Required. Allow one option only
Discharge from outpatient care/Lost to follow-up (SECTION/PAGE 9)		
Date of data entry into the database	DD/MM/YYYY	Required entry

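### The surgery, SRS and fRT form pages cannot hold last-follow-up performance status or total follow-up for patients who recur or progress, although section 3.8.3 asks for both

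*Protocol*

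**What the plan says.** Protocol section 3.8.3 lists separate items for operated patients. Follow-up duration in months is one. Performance status is another: "WHO performance status pre- and postoperatively and at the last follow-up appointment". Recurrence is a third: "Recurrence on contrast-enhanced MRI during that time (yes/no) and if recurred then the time to recurrence". The list for SRS and fRT runs in parallel: a duration of follow-up after radiation, "WHO performance status pre- and post-radiation and at the last follow-up appointment", and progression or regrowth with its timing. Section 3.8.4 again asks for follow-up durations among the overall outcomes.

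Appendix 1 turns these into form fields. On the surgery page, the recurrence tick box is followed by one date, "Scan date (at recurrence or last follow-up date if no recurrence", and one PS item, "WHO PS at time of recurrence/last follow-up", with options 0 to 4. The SRS and fRT pages have one date, "Scan date (at progression or last follow-up date if no progression", and one PS item, "WHO PS at time of progression/last follow-up", with options 0 to 5, where 5 means dead.

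**The concern.** The protocol body treats recurrence as something that happens within follow-up. The form treats it as the end of follow-up. A patient who recurs has two dates and two PS values of interest, but the form has room for one of each. When the final PS is measured then depends on the outcome: at the event for some patients, at the last visit for the rest.

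At stake is the description of how patients fare after intervention. Final PS pooled over treated patients would not be what section 3.8.3 defines, and post-treatment follow-up would be understated for anyone seen after recurrence or progression. No analysis can restore values that were never entered. Sites would have to go back to the records.

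**Working it through.** No figure in the protocol is in dispute, so the check sets section 3.8.3 against Appendix 1 item by item.

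| Asked for in section 3.8.3 | Surgery page | SRS and fRT pages |
|---|---|---|
| PS before treatment | field present | field present |
| PS after treatment | field present, 0 to 5 | no separate field |
| Timing of recurrence or progression | single date | single date |
| Last-follow-up PS, no event | single late PS item | single late PS item |
| Last-follow-up PS, event occurred | **no field** | **no field** |
| End of total follow-up, no event | single date | single date |
| End of total follow-up, event occurred | **no field** | **no field** |

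**Does the PS item follow the date item?** The slash in the PS label is ambiguous alone. The date label paired with it is not: it admits the last follow-up date only where there was no event. One PS value beside one date is naturally read by the same rule.

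**Does section 3.8.3 mean recurrence to end follow-up?** No. It records recurrence within the follow-up period and lists time to recurrence apart from the length of that period. The two coincide only if the patient is never seen again after recurring.

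**Can another page supply the missing values?** The page for discharge or loss to follow-up takes rescans, their outcome and vital status. The mortality page takes date and cause of death. Neither takes PS. As printed, the three treatment pages end at the late PS item, with no outcome field leading to a later page.

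**What follows for individual patients?** On the radiation pages, a patient who dies without progression can be entered as 5. One who progresses and later dies is entered with the PS at progression. On the surgery page the late item has no option for death. The SRS and fRT pages as printed also list no treatment date, from which post-radiation follow-up would be counted.

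**What uses these fields?** The nearest objective in section 2.2 concerns complications and recurrence or growth after intervention. PS after treatment is not an endpoint in section 3.5, and section 3.10 plans no analysis of it; the PS groups used there come from baseline.

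**Size.** The protocol gives neither a recurrence rate after treatment nor a rate of later decline. Suppose a share r of treated patients recur, and a share d of those decline between the recurrence date and last follow-up. The form then misses r × d of all treated patients. With assumed r of 5% to 20% and d of 10% to 50%:

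- low: 0.05 × 0.10 = 0.005, or 0.5 percentage points
- high: 0.20 × 0.50 = 0.10, or 10 percentage points

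The twenty-fold spread comes wholly from the assumptions and shows only that the size is unknown.

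**The case against.** The strongest reply is that the design is right for its main purpose. For time to recurrence, the event date if there was an event and the last follow-up date if not is the standard event-or-censoring date. Recurrence risk, the named objective, is therefore unharmed. That stands in full.

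Second, no planned analysis uses late PS, and the surgery page has its own required postoperative PS, whether or not the tumour later recurs. This also stands. For surgery only the later PS of recurrent patients is lost; for SRS and fRT there is no such second measurement.

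Third, Appendix 1 is a guide for database developers, and section 3.7 plans two testing phases before the tool goes live. The built form may differ. But the guide is the only specification shown, and as written it does not deliver section 3.8.3.

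Fourth, adding last-follow-up PS does not put all patients on a common time scale, since last visits also differ between patients. True: the change restores agreement with section 3.8.3 and removes the dependence of timing on the recorded event. It does not make patients fully comparable.

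**Conclusion.** The contradiction between section 3.8.3 and Appendix 1 is real and affects all three treatment pages. A form built as written cannot yield last-follow-up PS or total post-treatment follow-up for patients who recur or progress, and any summary of final PS would mix outcome-dependent time points. The effect is confined to descriptive post-treatment outcomes. Its size cannot be derived from the documents.

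A reader might go further and infer that functional outcome after treatment will look better than it is, because follow-up of PS stops in the very patients who decline. The documents do not support this. They do not say that PS falls after recurrence. Section 3.8.3 identifies recurrence on MRI, so it need not cause symptoms, and PS at recurrence already includes any decline present by then. Nor does the protocol plan to compare late PS between recurrent and non-recurrent patients or between treatments. The direction of any distortion is plausible but not established.

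The conclusion assumes that the PS item follows the same rule as its paired date and that the pages are complete as printed.

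**What to change.** On the surgery, SRS and fRT pages, split the shared fields:

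- date of recurrence or progression and PS at that date, shown only if the event is ticked;
- date of last follow-up and PS at that date, required for every treated patient, with a category for death on all three pages.

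Report final PS and length of follow-up from the second pair, and time to recurrence or progression as now. The same revision should settle the post-radiation PS that section 3.8.3 requests but the SRS and fRT pages omit.

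The cost is a few extra fields per treated patient, filled from records that sites already review, plus one sentence stating which fields feed the summaries. The testing phases in section 3.7 are the natural point to make the change.

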3.5. Study endpoints

3.5.1. Primary endpoint

Disease progression will be defined using a composite endpoint comprising of new symptom development, meningioma-specific mortality, meningioma growth (absolute growth rate ≥ 2 cm³/year or absolute growth rate ≥ 1 cm³/year + relative growth rate $\geq 30\%$ /year), development or increase of peritumoural brain oedema (defined as increased signal intensity on T2/FLAIR), venous sinus invasion and meningioma volume exceeding 10 cm³. The first two criteria denote clinical progression while the latter three are related to loss of window of curability. Venous sinus invasion and peritumoural oedema can prevent complete surgical resection (13, 14). Peritumoural oedema and a meningioma volume >10 cm³ are relative contraindications to stereotactic radiosurgery (15, 16).

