For patients discharged from outpatient care, data sources will be checked for any readmissions/rescans thought to be attributed to the incidental meningioma within the study timeframe; date of diagnosis up to the date of data entry. Outcome following readmissions/rescans will be noted.

Grade I	Any non–life-threatening deviation from normal postoperative course, not requiring invasive treatment
Grade Ia	Complication requiring no drug treatment
Grade Ib	Complication requiring drug treatment
Grade II	Complication requiring invasive treatment such as surgical, endoscopic, or endovascular interventions
Grade IIa	Complication requiring intervention without general anaesthesia
Grade IIb	Complication requiring intervention with general anaesthesia
Grade III	Life-threatening complications requiring management in ICU
Grade IIIa	Complication involving single organ failure
Grade IIIb	Complication involving multiple organ failure
Grade IV	Complication resulting in death
Surgical Complications	Adverse events that are directly related to surgery or surgical technique
Medical Complications	Adverse events that are not directly related to surgery or surgical technique
Suffix “T” (Transient)	New neurologic deficit improving within 30 days of surgical procedure; can be added to each grade of complication
Suffix “P” (Persistent)	New neurologic deficit extending beyond 30 days of surgical procedure; can be added to each grade of complication

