If yes, which	Dropdown list/check box 
 • Internal carotid artery • Basilar artery • Vertebral artery • Middle cerebral artery • Anterior cerebral artery • Posterior cerebral artery • Optic apparatus (optic nerve and chiasm) • Trigeminal nerve • Facial nerve • Vestibulo-cochlear nerve • Other 	Prompt entry if previous option (In contact with critical neuro-vascular structures?) has been ticked
Major axis (mm)	Free field	Required entry Note to data collector: In mm to 1 dp. Measure on axial T1/CT + GAD
Minor axis (mm)	Free field	Required entry Note to data collector: In mm to 1 dp. Perpendicular to the major axis on axial T1/CT + GAD
Cor/sag major axis	Free field	Require entry Note to data collector: In mm to 1 dp. Maximum height
Location	Dropdown list/Check box 
 • Convexity 	Required entry. Allow one option only Note to data collector: as per ICOM classification (appendix 2)

	
 • Parasagittal • Parafalcine • Sphenoid wing • Anterior midline • Post fossa-midline • Post fossa-lateral & posterior • Tentorial • Intraventricular • Pineal region 	
Location subcategory	Dropdown list/Check box 
 • Anterior • Posterior • Falco-tentorial • Lateral • Medial (including ACP) • Cribriform plate/olfactory groove • Planum • Tuberculum/diaphragma sellae • Clival • Petro-clival • Anterior foramen magnum • Petrous • Squamous occipital • Posterior foramen magnum • Supratentorial • Infratentorial 	Required entry. Allow one option only Note to data collector: ICOM classification (appendix 2) Appropriate subcategories will appear based on main category selected
Side	Dropdown list/check box 
 • Right • Left • Midline 	Required entry. Allow one option only
MANAGEMENT DECISION (PAGE/SECTION 4)		
Decision	Dropdown list/Check box	Required entry. Allow one option only

	
 • Active monitoring • Surgery • SRS • fRT • Discharge from outpatient care • Lost to follow-up • Dead 	Note to data collector: You will be directed to the relevant page/section dependent on the choice. If the patient died or was lost to follow-up after this point in time, please choose one of the last two options, albeit the intention might have been to continue monitoring or intervene.
ACTIVE MONITORING (SECTION/PAGE 5)		
Scan date	DD/MM/YYYY	Required entry

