Peritumoural signal intensity on T2	Dropdown list/check box 
 • 0-5% • 6-33% • 34-66% • 67-100% • NA 	Required entry. Allow one option only Note to data collector: In relation to tumour volume on T2/FLAIR MRI. If only CT or T1 MRI available, NA
Peritumoural signal intensity on FLAIR	Dropdown list/check box 
 • 0-5% • 6-33% • 34-66% • 67-100% • NA 	Required entry. Allow one option only Note to data collector: In relation to tumour volume on FLAIR MRI. If only CT or T1 MRI available, NA
Venous sinus nearby	Checkbox	Required entry. Note to data collector: Tick box if within 10 mm, in direct contact or invading one of: superior sagittal sinus (SSS), sigmoid sinus (SS), transverse sinus (TS), cavernous sinus (CS) and the confluence of sinuses (CoS)
If yes, specify	Dropdown list/check box 
 • Superior sagittal sinus • Cavernous sinus • Sigmoid sinus • Transverse sinus • Confluence of sinuses 	Prompt entry if previous option (venous sinus nearby) has been ticked. Allow one option only
Separate, direct contact or invaded?	Dropdown list/check box 
 • Separate • Direct contact • Invaded 	Prompt entry if previous option (venous sinus nearby) has been ticked. Allow one option only

Any new meningioma-related symptoms?	Checkbox	Required entry
If yes, specify domain	Dropdown list/check box 
 • Seizure • Headache • Motor • Sensory • Language • Cognitive • Other 	Prompt entry if previous option (Any new meningioma-related symptoms?) has been ticked. Allow multiple options
Major axis (mm)	Free field	Required entry Note to data collector: In mm to 1 dp. Measure on axial T1/CT + GAD if available
Minor axis (mm)	Free field	Required entry Note to data collector: In mm to 1 dp. Perpendicular to the major axis on axial T1/CT + GAD if available
Cor/sag major axis (mm)	Free field	Required entry Note to data collector: In mm to 1 dp. Maximum height

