Rescanned during the time between discharge/loss to FU and the date of data entry	Checkbox	Required entry
Date of scan	DD/MM/YYYY	Prompt entry if previous option (Readmitted/rescanned during the time between discharge/loss to FU and the date of data entry) has been checked
Reason?	Dropdown list: 
 • Seizure • Headache • Motor • Sensory • Language • Cognitive 	Prompt entry if previous option (Readmitted/rescanned during the time between discharge/loss to FU and the date of data entry) has been checked. Allow multiple options

	
 • Other 	
Peritumoural signal intensity on T2	Dropdown list/check box 
 • 0-5% • 6-33% • 34-66% • 67-100% • NA 	Prompt entry if previous option (Readmitted/rescanned during the time between discharge/loss to FU and the date of data entry) has been checked. Allow one option only Note to data collector: In relation to tumour volume. If only baseline CT available, NA
Peritumoural signal intensity on FLAIR	Dropdown list: 
 • 0-5% • 6-33% • 34-66% • 67-100% • NA 	Prompt entry if previous option (Readmitted/rescanned during the time between discharge/loss to FU and the date of data entry) has been checked. Allow one option only Note to data collector: In relation to tumour volume. If only baseline CT available, NA
Venous sinus nearby	Checkbox 
 • Superior sagittal sinus • Cavernous sinus • Sigmoid sinus • Transverse sinus • Confluence of sinuses 	Prompt entry if previous option (Readmitted/rescanned during the time between discharge/loss to FU and the date of data entry) has been checked Note to data collector: Tick box if within 10 mm, in direct contact or invading one of: superior sagittal sinus (SSS), sigmoid sinus (SS), transverse sinus (TS), cavernous sinus (CS) and the confluence of sinuses (CoS)
If yes, specify	Dropdown list/check box	Prompt entry if previous option (venous sinus nearby) has been ticked. Allow one option only
Separate, direct contact or invaded?	Dropdown list/check box 
 • Separate • Direct contact • Invaded 	Prompt entry if previous option (venous sinus nearby) has been ticked. Allow one option only

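### The Appendix 1 form has no field or date for a symptomatic readmission or a clinic visit without a scan, although section 3.8.3 asks for readmissions and for the outcome of each visit

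*Protocol*

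**What the plan says.** Protocol section 3.5.1 puts new symptoms first in the primary endpoint, with no imaging condition: "Disease progression will be defined using a composite endpoint comprising of new symptom development, meningioma-specific mortality, meningioma growth", followed by the imaging criteria.

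Section 3.8.3 sets out three collection duties:

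- Under active monitoring, symptoms are reviewed scan by scan: "Each scan will be examined alongside its corresponding outpatient clinic appointment for any evidence of meningioma-related symptoms".
- Separately, "The outcome of each clinical encounter (i.e. outpatient appointment) will be recorded". The options listed are management decisions, from continuing follow-up to treatment or discharge.
- For discharged patients, "data sources will be checked for any readmissions/rescans thought to be attributed to the incidental meningioma within the study timeframe". It adds: "Outcome following readmissions/rescans will be noted".

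Appendix 1 (section 9.1) turns these into form pages. Page 5, for active monitoring, opens with a required scan date and has three required tumour diameters. The symptom question, "Any new meningioma-related symptoms", and the outcome field sit inside that scan record. On Page 9, for discharged patients and those lost to follow-up, everything hangs on a box labelled "Rescanned during the time between discharge/loss to FU and the date of data entry".

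**The concern.** The form is what sites will fill in, and it is narrower than the text it implements. After discharge, section 3.8.3 names two kinds of event, and the controlling box on Page 9 names one. Under monitoring, section 3.8.3 wants the outcome of every encounter, and Page 5 accepts an encounter only if it came with a scan.

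Three uses of the data are at stake. Section 3.10.1 compares predicted with observed 5- and 10-year risk, and a symptom event that is missed, or dated at a later scan, lowers the observed curve or moves the event to the right, possibly past a horizon. The same section censors patients still under follow-up at their latest clinic appointment, and, in the intervention analysis, discharged patients when a physician last saw them. The form holds neither date unless it coincides with a scan. Section 3.10.4 costs clinic appointments as well as MRI scans, and an appointment without a scan has no row.

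**Working it through.** The main question is settled by comparing text.

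**Page 9 against section 3.8.3**

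1. Section 3.8.3 requires readmissions and rescans, with their outcome.
2. The gate on Page 9 mentions rescanning only.
3. The dependent fields (scan date, reason, imaging, diameters, related/unrelated verdict, outcome) are prompted by a 'Readmitted/rescanned' option. No field has that label, so the page also disagrees with itself.
4. The overall-outcome field opens when the 'Rescanned' box is empty and offers only dead or alive.
5. The only event date behind the gate is the date of the scan. If a site ticks the box for a readmission without a scan, the event still cannot be dated.

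Read literally, a discharged patient readmitted with a meningioma-attributed seizure and not rescanned is recorded as alive and nothing more.

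**Page 5 against section 3.8.3**

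1. The symptom review in section 3.8.3 is itself tied to each scan and its paired appointment, so placing the symptom field in the scan record agrees with that sentence.
2. The encounter-outcome sentence has no such tie. Page 5 has no visit date, and its required scan date and diameters leave no row for a visit without imaging.
3. A symptom found at such a visit can still surface later: at the next scan, with that scan's date; as a clinical or clinical-radiological indication with a surgery date (Page 6); or as a meningioma-related death (Page 10). The radiosurgery and radiotherapy pages (7 and 8) list neither an indication nor a treatment date.
4. The symptom is missed only if no scan, surgery or meningioma-related death follows.

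**Which analysis is affected**

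In the competing-risk analysis of progression (section 3.10.1), discharge and loss to follow-up are competing events. A later readmission comes after the patient's first event there and would not count even if recorded. The Page 9 gap therefore matters for the Kaplan-Meier validation, and only if events after discharge enter it. The protocol does not say whether they do.

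**Size**

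Inputs from section 3.4: at least 100 events, progression risk 10%, at least 1500 patients.

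- The plan's figure: 100 / 0.10 = 1000 patients, as stated.
- Expected events at the planned size: 1500 × 0.10 = 150.
- The documents give no share for symptom events without imaging. With an assumed missed share s, events = 150 × (1 − s) and crude observed risk = 10% × (1 − s):

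| Assumed s | Events | Observed risk |
|---|---|---|
| 5% | 142.5 | 9.5% |
| 10% | 135 | 9% |
| 20% | 120 | 8% |
| 30% | 105 | 7% |

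- Events fall below 100 only if s exceeds 1 − 100/150 = one third.

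These are crude proportions that ignore censoring. They show direction and scale and do not estimate the loss.

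**The case against.** The strongest reply is that the scan is the protocol's chosen unit for finding symptoms under monitoring, that Page 5 carries this out faithfully, and that Page 9 contains a labelling slip whose intent is clear from its own prompts. Appendix 1 is a guide for database developers, and section 3.7 plans two phases of testing before the form goes live. Most of this is fair. But the label is not the only gap on Page 9: the empty-box route and the missing event date would remain after a reworded prompt. The missing row for visits without a scan also conflicts with section 3.8.3 whatever is decided about symptom review.

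A reader might infer more than the documents support:

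- *That every symptom event without imaging is lost.* Under monitoring it may be entered late or appear as a surgical indication or a meningioma-related death.
- *That section 3.8.3 requires symptoms to be recorded at every visit.* It requires the visit's management outcome; symptom review is tied to scans.
- *That the comparison by performance status and ACCI is distorted by readmissions after discharge.* The progression analysis treats discharge as a competing event, and the other analysis has intervention as its endpoint.
- *That patients followed by CT lose their symptom events.* Page 5 accepts CT measurements and offers NA for signal intensity.
- *That clinic-only visits are costed at zero.* Section 3.10.4 does not say how appointments are counted, so undercounting is possible but not stated.

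The net effect on calibration also depends on how symptoms were found in the cohort used to build the model, which these documents do not describe.

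**Conclusion.** The point holds in this form. Page 9 contradicts section 3.8.3 and itself, leaving a symptomatic readmission without a scan with no field and no date. Page 5 cannot take the date or outcome of a visit without a scan, and a symptom found there is misdated or, in some patients, missed.

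The direction is downward for observed progression risk, or late for event times, in the Kaplan-Meier validation. For events after discharge this depends on their being counted, which should be stated. The size cannot be derived from the documents; the 9.5 to 9% range rests on an assumed missed share of 5 to 10%. The 100-event minimum is not at risk unless more than a third of events are missed. The possible undercount of clinic-only appointments concerns a secondary objective. Because a component of the primary endpoint is affected and the repair is small, the change should be made.

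**What to change.** On Page 9, change the gate to 'Readmitted or rescanned', with matching wording in every dependent prompt and in the condition that opens the dead/alive field. Add an event date separate from the scan date. Show the imaging fields only if a scan was done, and keep reason, verdict and outcome open for both kinds of event.

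On Page 5, add an encounter date and an encounter type (scan with clinic, clinic only, emergency attendance), and require scan date and diameters only when there was a scan. Date a meningioma-attributed symptom at the encounter where it was found.

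In section 3.10.1, state whether events after discharge count in the Kaplan-Meier observed risks.

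The cost is a set of REDCap field and branching edits and a few more entries per patient, from notes that sites already review. If data entry has begun, records already entered for discharged patients and for visits without a scan would need a second look.
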